7.3.4. Study Day

In the analyses described in this SAP, whenever possible, actual study day based on calendar days relative to Day 1 will be used whenever “study day” is mentioned. In cases where calendar date is not available, e.g. imputed instances, nominal days will be used.

7.3.5. Pooling of Investigational Sites

The data from all study centers will be pooled together for all planned analyses.

7.3.6. Coding Conventions for Events and Medications

All adverse events, and medical history will be mapped to the Medical Dictionary for Regulatory Activities (MedDRA Version 24.0) system for reporting (preferred term and body system).

Prior and Concomitant medications will be coded using WHO-DD (Drug Dictionary) (Version C3 Format- Mar 1, 2021).

7.3.7. Analysis Software

Data manipulation, tabulation of descriptive statistics, calculation of inferential statistics, and graphical representations will be performed primarily using SAS (release 9.4 or higher) for Windows. PK parameterization will be performed via WinNonlin[®]. If the use of other software is warranted, the final clinical study report will detail what software was used and for what purposes.

[figure not shown]
7.3.8. Study Data

Study data identified in the schedule for time and events (Table 1) are collected, and source verified, on the electronic data capture tool: Fusion eClinical Suites. Laboratory and efficacy data are provided from external laboratories and uploaded into the EDC.

Study data will be formulated into regulatory compliant data sets to provide transparency, traceability, and integrity of trial analysis results from the collection source. Observed study data will be mapped to the CDISC Study Data Tabulation Model (SDTM) and serve as the source data from the trial. All study analyses will be completed using analysis data sets that are derived from the SDTM and follow the CDISC Analysis Data Model (ADaM) architecture.

The methods for programming the CDISC SDTM and ADaM data sets are described in Figure 1.

Figure 1 SDTM, ADaM, and TFL Development and Validation

Where:

1. Development, Validation, and Maintenance of SDTM Domains
2. Development and Validation of Analysis Data Sets (ADaM), with input source the appropriate SDTM domains

3. Development and Validation of Tables, Figures, and Listings (TFL), with input data source the SDTM domains and analysis specific ADaM data sets

7.4. Planned Study Analyses

7.4.1. Statistical Summaries: Descriptive and Inferential

There will be no formal hypothesis testing for this study. All p-values shown from exploratory analyses will be rounded to and displayed in four decimals. If a p-value less than 0.0001 occurs it will be shown in tables as <0.0001.

Descriptive summaries of variables will be provided where appropriate. For continuous variables, the number of non-missing values (n), mean, standard deviation, median, minimum, and maximum will be tabulated by treatment. For categorical variables, the counts and proportions of each value will be tabulated by treatment. Expansion of descriptive table categories within each treatment may occur if such elaborations are thought to be useful.

7.4.2. Data Safety Monitoring Board (DSMB)

An independent DSMB will perform reviews of unblinded safety, tolerability, and immunogenicity data from each cohort and ad hoc, per Sponsor request, if a pattern of unexpected, clinically significant trends or changes in other safety assessments is identified through blinded safety data reviews. The analyses required by the DSMB will be detailed in the DSMB Charter.

7.4.3. Interim Analysis

No Interim analysis will be performed.

7.4.4. Criteria for Pausing Enrollment

In the event a serious unexpected suspected adverse reaction (SUSAR) has occurred, the enrollment and initiation of study drug administration to new patients will be paused and the Sponsor will request an unblinded review by the DSMB, who will provide its recommendation to aTyr Pharma. Such recommendation may include, but is not limited to, stopping an ongoing cohort, stopping further dose escalation, continuing the study as planned, or continuing the study with modifications, such as evaluation of a lower or intermediate dose in the next cohort(s) to gain more information on safety and tolerability.

7.4.5. Final Analysis and Publication of Study Results

The final analyses detailed in this document will be completed after all patients have terminated from this study.

aTyr Pharma, Inc.
Study ATYR1923-C-002 Statistical Analysis Plan
IND#: 133692

FINAL Version 1.0
2021-08-02

7.5. Multiple Testing Procedures

Statistical tests performed in this study are exploratory, and no adjustments for multiplicity will be performed.

8. SUMMARY OF STUDY DATA

Unless otherwise specified, summaries will be presented by treatment arms, presenting all active arms individually, in addition to combined placebo arm and combined active arm.

8.1. Disposition

Patient disposition will be summarized and listed. All percentages will be based on the number of patients randomized in each arm.

The number of patients randomized by each site will be summarized. End of treatment and end of study information for all patients with a randomization number (randomized patients) will be summarized in this table, including the number of patients completing the study and the number of patients who terminated prematurely from the study, with reasons for withdrawal. The number of patients in each analysis set will also be summarized. The impact that COVID-19 had on patient disposition will also be summarized.

8.2. Protocol Deviations

Protocol deviations will be reported through EDC, and all information collected will be included in the SDTM.DV domain (deviations domain).

All patient-level protocol deviations will be presented in a data listing. A summary table will be generated based on the classification of patient-level protocol deviations.

8.3. Demographics and Baseline Characteristics

Patient demographic data as taken at screening, including age (continuous and categorical 18-64 and 65+), sex, ethnicity, and race will be summarized.

Baseline characteristics as collected on Day 1, including weight (kg), height (cm), BMI (kg/m^2), Baseline Dyspnea Index total score, Baseline Modified MRC Dyspnea scale score, key lung function variables, Sarcoidosis diagnosis at screening (all organ systems involved), and duration of disease will be summarized.

Also to be summarized are anti-sarcoidosis treatment at baseline (refer to Section 7.3.1 for baseline definition) including OCS type and dose categories (10 mg/day to <15 mg/day, 15 mg/day to <20 mg/day and 20 mg/day or higher), oral immunomodulator type at the time of baseline using the same baseline definition.

The demographic data and baseline characteristics will be summarized for the Safety, mITT and EE Sets. If they are the same, only mITT tables are needed.

aTyr Pharma, Inc.
Study ATYR1923-C-002 Statistical Analysis Plan
IND#: 133692

FINAL Version 1.0
2021-08-02

A patient's age in years is calculated as (date of screening - date of birth)/365.25. BMI is calculated by dividing the weight of patient screening in kg by the square of their height in meters.

8.4. Concurrent Illness and Medical Conditions

The number and percentage of patients with individual concurrent illness and medical histories will be summarized. Individual patient listings will also be provided for concurrent illness and medical history.

Concurrent illness and medical history will be coded using the MedDRA Version 24.0. The number and percentage of patients with any medical history will be summarized overall and for each system organ class (SOC) and preferred term (PT). Percentages will be calculated based on number of patients in the Safety Set.

Patient medical history data including specific details will be presented in a listing.

8.5. Prior and Concomitant Medications

The number and percentages of concomitant medications and prior medications that are ongoing at the start of study drug will be summarized by Anatomical Therapeutic Chemical (ATC) level 2 and PT. The total number of prior/concomitant medications and the number and percentages of patients with at least 1 medication will be summarized. All summaries will be performed using the Safety Set. Similarly, non-OCS sarcoidosis medications will be summarized separately.

A listing will present all prior and concomitant medications. Non-OCS sarcoidosis medications will be presented in a separate listing.

A concomitant medication is defined as any medication taken on or after the day of first exposure to study drug up until 30 days after last dose of study drug.

A Prior medication is defined as any medication that the patient is started and stopped prior to the day of first exposure to study drug, collected from up to 30 days prior to Screening.

If a medication has a missing start date, then it is conservatively assumed to be both prior and concomitant only.

8.6. Non-Medication Therapies/Treatments

All non-medication therapies and treatments will be listed as collected using the Safety Set.

aTyr Pharma, Inc.
Study ATYR1923-C-002 Statistical Analysis Plan
IND#: 133692

FINAL Version 1.0
2021-08-02

8.7. Treatment Administration and Exposure

Study drug will be administered at the study center. To ensure treatment compliance, administration of the study drug will be supervised by the Investigator or authorized designee.

The number of fully administered doses and total dose infused (as calculated by the sum of all administered doses in mg) will be summarized and listed.

An exposure summary will be conducted using the Safety Set.

9. SAFETY ANALYSES

All Safety analyses will be conducted using the Safety Set.

9.1. Adverse Events

Adverse events will be coded using the Medical Dictionary for Regulatory Activities (MedDRA), version 24.0. Adverse events will be recorded from the date of informed consent, throughout the clinical trial.

Treatment-emergent adverse events (TEAEs) are defined as any adverse event or worsening of an existing condition after initiation of the investigational product and through 30 days after the patient's last study visit (study completion or early termination).

If the onset of an AE is on Day 1, then the time of first dose, collected from the Study Drug Administration CRF, will be compared to the time of onset to determine if the AE is treatment-emergent. If the start time is reported as "unknown", the AE is classified as TEAE.

The number and percent of patients with any TEAEs as well as number of TEAEs will be summarized by system organ class and preferred term by treatment and overall. At each level of tabulation (ex. at the preferred term level) patients will be counted only once if they had more than one such event reported during the AE collection period.

Level of intensity will be assessed using the CTCAE grading.

The following summary tables and patient level listings will be presented for AE data:

- Overall summary of TEAEs, including the number and percentage of the following: any TEAEs, treatment-related TEAEs, Serious TEAEs, TEAEs leading to study drug withdrawal, leading to study drug interruption, TEAEs leading to deaths, Grade 3 or 4 TEAEs, TEAEs suspected to be infusion related;
- Summary table of TEAEs by SOC and PT;
- Summary table of TEAEs by PT;

- Summary table of TEAEs by highest relationship level to study drug by SOC and PT;
- Summary table of TEAEs by maximum intensity by SOC and PT;
- Summary table of serious TEAEs by SOC and PT;
- Summary table of suspected infusion related TEAEs by SOC and PT;
- Listing of suspected infusion related TEAEs;
- Listing of all Non-Treatment-Emergent AEs;
- Listing of all TEAEs;
- Listing of AEs leading to study drug interruption;
- Listing of AEs leading to study drug withdrawal;
- Listing of AEs leading to death;
- Listing of TEAEs of grade 3 or 4;
- Listing of Serious TEAEs.

In summary tables, missing data are imputed per rules established in Section 7.3.3.1.

9.2. Clinical Laboratory Evaluations

Clinical laboratory results will be summarized descriptively for each treatment group by timepoint for the observed value as well as for the change from baseline value. In addition, laboratory shift tables will be provided for all laboratory parameters where low/normal/high or abnormal/normal status can be ascertained. Listings of individual laboratory parameters by visit with normal ranges and abnormality assessments will also be provided.

In addition, since anticoagulation medication may affect coagulation parameters, each record will be examined by medical monitor. Coagulation parameters of Subjects with concomitant medications of warfarin sodium, apixaban, rivaroxaban between screening and end of treatment are excluded for all visits.

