Table 1: Schedule of Assessments

Study Period							Tr	eatment							
Visit Study Day	Screen -28 to - 1	1 D1	1a W1/ D8	2 W2/ D15	2a W3/ D22	3 W4/ D29	3a, 3b, 3c W5, 6, 7	4 W8/ D57	4a W10/ D71	5 W12/ D85	5a W14/ D99	6 W16/ D113	6a W18/ D127	7 W20/ D141	EOS WK24/ D169
Visit Window (Days)	-	-	-	±2	±3	±3	±2	±3	±3	±3	±3	±3	±3	±3	±3
Written informed consent	X														
Telephone Contact			X		X		X		X		X		X		
Eligibility check	X	X													
Demographics	X														
Medical history	X														
Height & weight ¹	X	X				X		X		X		X		X	
Modified MRC Dyspnea Scale	X														
Physical examination ²	X									X					X
Vital signs ³	X	X		X		X		X		X		X		X	X
Pulse oximetry ⁴	X	X				X		X		X		X		X	X
12-lead ECG ⁵	X	X ⁵				X		X		X ⁵		X		X ⁵	X
Pulmonary Function Tests ⁶	X	X				X		X		X		X		X	X
DLco ⁷		X								X				X	X
Pregnancy test (females only) ⁸	X (serum)	X						X				X			X (serum)
Serum FSH ⁹	X														
Rheumatoid factor		X													
Jo-1 antibody (serum)	X			X		X		X		X		X		X	X
ADA sampling (serum) for anti- ATYR1923 antibodies ¹⁷	X			X		X		X		X		X		X	X
Safety laboratory testing (hematology, clinical chemistry)	X	X		X		X		X		X		X		X	X
Urinalysis ¹⁰	X	X		X		X		X		X		X		X	X
Coagulation laboratory testing (PT, INR, PTT)	X					X		X		X		X		X	X
Serology (HBsAg, anti-HCV, and anti-HIV 1/2 tests)	X														

Study Period							Tr	eatment							
Visit Study Day	Screen	1 D1	1a W1/ D8	2 W2/ D15	2a W3/ D22	3 W4/ D29	3a, 3b, 3c W5, 6, 7	4 W8/ D57	4a W10/ D71	5 W12/ D85	5a W14/ D99	6 W16/ D113	6a W18/ D127	7 W20/ D141	EOS WK24/ D169
Visit Window (Days)	-	-	-	±2	±3	±3	±2	±3	±3	±3	±3	±3	±3	±3	±3
Serum complement, serum tryptase, and IgE ¹¹		X													
Plasma complement ¹¹		X													
¹⁸ F-FDG-PET/CT (optional) ¹²	X											X			
Skin lesion visual assessments (if applicable) ¹³	X			X		X		X		X		X		X	
Skin lesion biopsy (optional for patients at select sites) ¹⁴	X									X					
AE assessment/Concomitant medications		X	X	X	X	X	X	X	X	X	X	X	X	X	X
Randomization ¹⁵		X													
King's Sarcoidosis Questionnaire		X				X		X		X		X		X	X
Leicester Cough Questionnaire		X				X		X		X		X		X	X
Baseline/Transitional Dyspnea Indices		X				X		X		X		X		X	X
Fatigue Assessment Scale		X				X		X		X		X		X	X
Sarcoidosis Assessment Tool		X				X		X		X		X		X	X
Blood sampling (serum) for ATYR1923 PK ¹⁶		X ¹⁶		X		X		X		X		X		X ¹⁶	X
PBMC collection ¹⁸		X								X					X
Serum biomarkers ¹⁹		X								X				X	X
Infusion site examination ²⁰		X				X		X		X		X		X	

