7.1.6. Concomitant Medication and Other Restrictions During the Study

7.1.6.1. Prohibited or Restricted Concomitant Medications and Substances

The following treatments and procedures are prohibited prior to and/or during study participation, as indicated below:

- Immunomodulatory agents, such as TNF-α inhibitors (eg, infliximab, adalimumab), are prohibited from 4 months of Day 1 and through the duration of study drug treatment.
- Live vaccination within 8 weeks before Day 1 and during study participation is prohibited.
- All investigational agents or devices (other than ATYR1923) within 3 months for small molecules and 6 months for biologics, or 5 half-lives (if known) of the agent, whichever is longer, before the first study drug dose and through the duration of study drug treatment.
- Major surgeries are prohibited from 3 months before the first study drug dose through the duration of study drug treatment.

- Heavy smoking/inhalation of tobacco/nicotine-containing products >20 cigarettes/day or e-cigarette equivalent.
- Topical treatment of any lesion identified by the Investigator for cutaneous assessments (eg, biopsy).

All other concomitant medications and procedures are allowed.

Concomitant medications are to be recorded in the source documents and in the eCRF.

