7.3.3. Missing Data

In general, missing data will not be imputed, unless methods for handling missing data are specified. All study related data that is collected will be included in data listings that will accompany the clinical study report.

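### SAP 9.2 drops a patient's coagulation results at every visit once one of three anticoagulants is used, so a mid-study start removes unaffected earlier results from the summary and shift tables

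*SAP*

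**What the plan says.** SAP 9.2 plans tables and listings for all laboratory data: "Clinical laboratory results will be summarized descriptively for each treatment group by timepoint for the observed value as well as for the change from baseline", together with shift tables, and "Listings of individual laboratory parameters by visit with normal ranges and abnormality assessments will also be provided".

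It then adds a special provision for coagulation. The reason and a review step come first: "since anticoagulation medication may affect coagulation parameters, each record will be examined by medical monitor". The rule follows: "Coagulation parameters of Subjects with concomitant medications of warfarin sodium, apixaban, rivaroxaban between screening and end of treatment are excluded for all visits". The SAP gives no criterion by which the medical monitor would keep a record, and it does not link the rule to the anticoagulant's start or stop date.

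Four other places bear on this:

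- **Protocol 7.1.6.1** does not list anticoagulants among prohibited treatments and ends with "All other concomitant medications and procedures are allowed". A start during the study is therefore possible.
- **Protocol 10.1.2.3.2** plans a summary of all out-of-range laboratory data and mentions no anticoagulant exclusion. SAP 3.3, which lists changes from the protocol's analysis, does not mention one either.
- **SAP 7.3.3** says "All study related data that is collected will be included in data listings that will accompany the clinical study report".
- **SAP 8.5** says "A concomitant medication is defined as any medication taken on or after the day of first exposure to study drug", running to 30 days after the last dose. The window in SAP 9.2 instead opens at screening.

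**The concern.** Some exclusion is reasonable, because anticoagulants change PT, INR and PTT directly. That reason reaches only samples drawn while the anticoagulant could be acting. It gives no ground for removing samples drawn before the anticoagulant was started.

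The rule also makes a patient's presence in the coagulation tables at every visit, including Screening, depend on something that can happen after randomisation. An anticoagulant might be started because of a new thrombotic event. In that case the tables would omit the earlier on-study coagulation results of a patient in whom those results are of particular interest. With 8 patients per dose arm, one omission is visible in every row of the table.

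**Working it through.** The plan states no figure on this point, so there is none to reproduce. The check is a count.

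**Inputs**

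- Coagulation samples (Table 1 of both documents): Screening and Weeks 4, 8, 12, 16, 20 and 24. That is 7 samples, 6 of them after first dose. There is no Day 1 sample, so Screening is normally the baseline.
- Parameters per sample: 3 (PT, INR, PTT).
- Dosing-day samples are taken pre-dose (Table 1, general note).
- Patients (Protocol 5 and 7.1.3): 8 active per cohort, 24 active in total, 12 placebo in total. SAP 8 presents each active arm, pooled active and pooled placebo.

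**Samples drawn before the anticoagulant.** A rule based on dates would keep these. The SAP 9.2 rule keeps none of them.

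| Anticoagulant starts | Unaffected samples (of 7) | Of which after first dose (of 6) | Post-dose values (× 3) |
|---|---|---|---|
| Before Screening, used throughout | 0 | 0 | 0 |
| After Day 1, before Week 4 | 1 | 0 | 0 |
| After Week 4 sample | 2 | 1 | 3 |
| After Week 8 sample | 3 | 2 | 6 |
| After Week 12 sample | 4 | 3 | 9 |
| After Week 16 sample | 5 | 4 | 12 |
| After Week 20 sample | 6 | 5 | 15 |

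The last row assumes that the start still falls before end of treatment.

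**Weight of one patient at each visit:** 1/8 = 12.5% of a dose arm; 1/12 = 8.3% of pooled placebo; 1/24 = 4.2% of pooled active.

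**Chance that it arises.** Neither document gives an anticoagulant start rate. Let p be the assumed probability that a patient starts one. The chance of at least one such patient among n is 1 − (1 − p)^n:

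| Assumed p | n = 8 | n = 24 | n = 36 |
|---|---|---|---|
| 1% | 7.7% | 21.4% | 30.4% |
| 3% | 21.6% | 51.9% | 66.6% |
| 5% | 33.7% | 70.8% | 84.2% |
| 10% | 57.0% | 92.0% | 97.7% |

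These show only that the case cannot be ruled out. They do not estimate how many patients were affected.

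**Where the window closes.** SAP 9.2 does not define end of treatment, and two readings are open:

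- The protocol synopsis describes a 20-week treatment period. On that reading the window closes around the last infusion, nominally Day 141, and a start between then and the Week 24 sample (Day 169) would not trigger the rule.
- SAP 3.3 and 10.1.3 use a dosing period ending 30 days after the last dose, and 10.1.3 appears to use end of treatment for the same thing. That gives Day 141 + 30 = Day 171, so a Week 24 visit on its nominal day falls inside.

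**The case against.** The strongest defence is that little depends on these tables. The study is descriptive, with no formal hypothesis testing (SAP 7.4.1). Keeping the same patients at every visit is a defensible choice for a descriptive table. A record-level rule would still remove later values because of the same post-randomisation event. All of this stands, and it keeps the point small. It does not explain why values that an anticoagulant could not have affected should be dropped.

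A reader might draw stronger conclusions, which the documents do not support:

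- **That the results disappear from the report.** SAP 9.2 and 7.3.3 provide listings of individual and of all collected data. With 36 patients these can be read in full.
- **That the primary endpoint is compromised.** It is the incidence of TEAEs and SAEs (SAP 4.2.1). A clot would still be counted in the SAP 9.1 tables, and Protocol 8.5.9 has clinically significant laboratory deviations recorded as adverse events.
- **That anticoagulant-affected Week 24 values stay in.** This depends on an undefined term. On the 30-day reading a Week 24 visit on schedule is covered.
- **That only the three named drugs can ever be considered.** The medical monitor's review of each record is not limited to them, although it has no stated criterion.
- **That patients were lost, or lost unequally between arms.** No start rate is given, and the number could be zero.

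**Conclusion.** The point holds in a narrow form and is minor. For a patient who starts warfarin sodium, apixaban or rivaroxaban mid-study, the rule removes unaffected earlier PT, INR and PTT results from the summary and shift tables, and no other provision puts them back. The size depends on the start date: between one and six unaffected samples for a start after first dose, and five of seven in the Week 16 example. For a patient anticoagulated from Screening onwards the rule costs nothing interpretable.

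This rests on the plain reading of SAP 9.2, on the exclusion applying to tables and not listings, and on at least one patient starting a named drug during the study, which the documents neither show nor exclude.

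**What to change.** Amend SAP 9.2 before unblinding:

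1. Exclude by record. Remove only PT, INR and PTT values dated from the first day of any anticoagulant through its stop date plus a washout stated in the SAP. Identify anticoagulants from the medication coding already planned in SAP 7.3.6 and 8.5, so that the rule does not depend on three names.
2. Keep all earlier values, including Screening.
3. Define end of treatment so that the rule clearly covers the Week 24 sample.
4. State the criterion for the medical monitor's record review.
5. Footnote the number of patients and values excluded, by arm.
6. Confirm that the listings keep every value, with a flag on those excluded from tables.

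The cost is SAP wording and a date merge of laboratory and medication records already collected. The downside is that n will vary slightly from visit to visit.
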